#### 9.3. Disease-Related Events or Outcomes Not Qualifying as AE/SAEs

Not applicable

#### 9.4. Monitoring and Recording of AEs and SAEs

#### 9.4.1. **Adverse Events**

Any AE experienced by the subject from Visit 4b (Randomization/Insertion) through Visit 9 (30 day follow-up visit) is to be recorded in the eCRF, regardless of the severity of the event or its relationship to study treatment.

Any AEs already documented at a previous assessment and designated as ongoing, should be reviewed at subsequent visits as necessary. If these have resolved, this should be documented. Changes in intensity or frequency of AEs should be recorded as separate events (i.e., a new record started).

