#### 9.7. **Evaluating AEs and SAEs**

#### 9.7.1. Severity

The following definitions should be considered when evaluating the severity of AEs and SAEs:

- Mild Event is noticeable to the subject, but is easily tolerated and does not interfere with the subject's daily activities
- Event is bothersome, possibly requiring additional therapy, and • Moderate may interfere with the subject's daily activities
- Severe Event is intolerable, necessitates additional therapy or alteration of therapy, and interferes with the subject's daily activities

For AEs that change in intensity, the start and stop date of each intensity should be recorded.

An AE that is assessed as severe should not be confused with a SAE. An event is defined as 'serious' when it meets one of the pre-defined outcomes as described in Section 9.2 "Definition of a SAE."

CLN-Protocol-0052 Page **37** of **61** 

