13.1 Adverse Events

An AE is any untoward medical occurrence in a patient or clinical investigation subject administered a pharmaceutical product and that does not necessarily have a causal relationship with the treatment. An AE can therefore be any unfavorable and unintended sign (including an abnormal laboratory finding), symptom, or disease temporally associated with the use of an IP, whether or not related to the IP. Treatment-emergent adverse events (TEAE) are defined as AEs that occur after the first use of IP. Per the protocol, only AEs that begin or worsen after insertion of the IP will be captured in the database for this study; therefore, TEAEs and AEs are equivalent in this study and will be denoted as AEs.

All AEs will be assigned a severity grade of mild, moderate, or severe based on the following definitions:

- *Mild:* Event is noticeable to the subject, but is easily tolerated and does not interfere with the subject's daily activities.
- *Moderate:* Event is bothersome, possibly requiring additional therapy, and may interfere with the subject's daily activities.
- Severe: Event is intolerable, necessitates additional therapy or alteration of therapy, and interferes with the subject's daily activities.

An AE is considered serious if, in the view of either the Investigator or Sponsor, it results in any of the following outcomes:

- Death
- A life-threatening AE
- Inpatient hospitalization or prolongation of existing hospitalization
- A persistent or significant incapacity or substantial disruption of the ability to conduct normal life functions
- A congenital anomaly/birth defect

Important medical events that may not result in death, be life-threatening, or require hospitalization may be considered serious when, based upon appropriate medical judgment, they may jeopardize the subject and may require medical or surgical intervention to prevent one of the outcomes listed above.

Documentation of AEs will include onset date, resolution date, location (OD, OS, both eyes [OU], nonocular), severity, action(s) taken, IP relationship, outcome, seriousness, reason for seriousness, expectedness, action taken with IP, and a description/narrative of the AE. All AEs will be coded using MedDRA classifications with reference to SOCs and PTs (MedDRA, version 20.0).

An overall summary table of AEs will be presented to report the number of AEs and the numbers and percentage of subjects who experienced at least one AE in the following categories:

- AEs

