- Ocular AEs
- Non-Ocular AEs
- SAEs
- AEs by Severity
- AEs Leading to Subject Withdrawal
- AEs Resulting in Death

Additional AE summary tables will be presented by treatment and for all subjects showing the number of AEs and the number and percentage of subjects who experienced at least one AE. These summaries will be presented at the subject level by SOC and PT. If a subject reports multiple AEs coded the same SOC and/or PT, that SOC and/or PT will only be reported once. For AE summaries by severity or relationship to IP, if a subject reports multiple AEs coded to the same PT within a given SOC, the subject will be counted once under the maximum (worst) severity or relationship to IP as applicable. In the summaries, SOC will be listed in order of descending frequency for all subjects; PTs will be listed in order of descending frequency for all subjects; and non-ocular AEs separately and include the following:

- All AEs
- All AEs suspected to be related to the IP
- All SAEs suspected to be related to the IP
- All AEs by Relationship to IP
- All AEs by Severity

Subject listings will be provided for all AEs, SAEs, AEs leading to death, and AEs leading to study treatment discontinuation.

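### An adverse event that changes in intensity or frequency is split into several records, and the SAP counts each record as an AE in its event totals

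*Protocol*

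**What the plan says.** **Recording.** Protocol 9.4.1 (Adverse Events) instructs: "Changes in intensity or frequency of AEs should be recorded as separate events (i.e., a new record started". The rule is not limited to worsening, so improvement and any change in frequency, up or down, also open a new record. Protocol 9.7.1 (Severity) adds: "For AEs that change in intensity, the start and stop date of each intensity should be recorded".

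**Counting.** Under SAP 13.1 the overall AE table is to "report the number of AEs and the numbers and percentage of subjects who experienced at least one AE in the following categories", and AEs by severity is one of those categories. The additional tables are described as "showing the number of AEs and the number and percentage of subjects who experienced at least one AE".

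**De-duplication.** SAP 13.1 has two once-only rules, both framed at subject level. For SOC and PT: "If a subject reports multiple AEs coded the same SOC and/or PT, that SOC and/or PT will only be reported once". For the severity and relationship tables: "the subject will be counted once under the maximum (worst) severity or relationship to IP as applicable". Neither document has a rule that joins successive records of one event before events are counted.

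**Database content.** SAP 13.1 states that, per the protocol, "only AEs that begin or worsen after insertion of the IP will be captured in the database for this study", and on that basis treats AEs and treatment-emergent AEs as the same thing.

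**The concern.** A reader takes a column headed number of AEs to show how many events occurred. Under this plan it shows how many records were opened. The two agree for an AE that never changes and differ for one that does. The gap depends on how much events fluctuate and on how closely a site tracks them. Sites have many chances to note a change: the Time and Event Schedule assesses AEs at eight visits from insertion to exit (4b, 5, 6a, 6b, 7, 8a, 8b, 9), with two pairs of visits about eight hours apart, and the protocol sets no threshold for a change in frequency.

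Two outputs are exposed. One is the event total per arm, a figure that Protocol 4.2 quotes for each of the three earlier allergic conjunctivitis studies. The other is the event-level severity split in the overall table. A moderate event that starts and ends mild contributes two mild AEs and one moderate AE, so the mix looks milder than the single moderate episode that occurred.

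**Working it through.** The documents give no figure for the effect of record splitting, so there is nothing of the plan's own to reproduce. The check is a counting identity, followed by an illustration on the totals that the protocol quotes.

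**1. Records per event.** Let k be the number of recorded changes in one event. Under Protocol 9.4.1, records = k + 1 and subjects = 1.

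| Changes k | AEs counted | Subjects counted |
|---|---|---|
| 0 | 1 | 1 |
| 1 | 2 | 1 |
| 2 (e.g. mild, moderate, mild) | 3 | 1 |
| 3 | 4 | 1 |

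**2. Effect of the SAP's database statement.** That statement covers AEs that begin or get worse. If it acted as a filter, only the w worsening steps would add records, giving w + 1. For mild, moderate, mild, w = 1, so the count is 2, not 3. The event is still counted more than once, and the documents do not settle which count applies. The statement is presented as a description of what the protocol captures, and Protocol 9.4.1 captures more than that.

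**3. Effect on a total.** Let f be the share of events that change and c the mean number of changes among those. Reported events / actual events = 1 + f × c. The documents give neither f nor c. With assumed values:

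- f = 10%, c = 1: 1 + 0.1 × 1 = 1.1, so 10 events are reported as 11.
- f = 20%, c = 2: 1 + 0.2 × 2 = 1.4, so 10 are reported as 14.
- f = 30%, c = 2: 1 + 0.3 × 2 = 1.6, so 10 are reported as 16.
- f = 0: ratio 1.0, no effect.

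For subject counts and percentages the ratio is 1.0 throughout.

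**4. Scale against the earlier studies (Protocol 4.2).** Take each quoted total as if it were a count of distinct episodes, and suppose one event with two changes, which adds two records.

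| Study and arm | AEs | Subjects with AEs | AEs per subject | Two extra records |
|---|---|---|---|---|
| Phase 2, OTX-DP | 14 | 11 | 1.27 | 2/14 = 14% |
| Phase 2, vehicle | 12 | 10 | 1.20 | 2/12 = 17% |
| First Phase 3, OTX-DP | 4 | 3 | 1.33 | 2/4 = 50% |
| First Phase 3, vehicle | 7 | 4 | 1.75 | 2/7 = 29% |
| Second Phase 3, OTX-DP | 7 | 6 | 1.17 | 2/7 = 29% |
| Second Phase 3, PV | 17 | 11 | 1.55 | 2/17 = 12% |

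Across the Phase 3 arms the illustration runs from 12% to 50%. The totals serve only as a scale for what one split event would do. Whether those studies used this recording rule is not stated.

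**The case against.** The case against giving this much weight is strong, and most of it stands.

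- **The main safety measure is safe.** The SOC and PT tables are built on subjects, and the severity and relationship tables take the worst grade per subject. SAP 13 plans no inferential testing of safety, so no p-value depends on an event total. This stands and limits the point to descriptive columns.
- **The rule is the same in both masked arms.** This stands. A reader might infer that the comparison of arms is biased. The documents do not show that; it would need events to fluctuate more, or be tracked more closely, in one arm.
- **There may be little splitting.** The earlier arms had 1.17 to 1.75 AEs per affected subject, including events that were truly distinct. In the arm with 4 AEs in 3 subjects, at most one record could have been a repeat. This is fair as a guide to scale, although the rule used there is unknown.
- **Raised IOP is not a good example.** A reader might expect lasting events such as raised IOP to be inflated most. After insertion IOP is scheduled only at Visits 6b, 8b and 9. Severity in Protocol 9.7.1 rests on tolerability, need for therapy and interference with daily life, not on mmHg. SAP 13.4 also summarises IOP separately.
- **Protocol 9.7.1 does not contradict 9.4.1.** Dating each intensity is compatible with separate records, and 9.7.1 does not say that the phases form one event.
- **Records can be traced.** AE documentation includes dates, severity and outcome, and all AEs are listed, so a reader could rebuild episodes by hand. That helps a careful reader of the listings but does not correct the tables.

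One might also read the SOC/PT once-only rule as covering event counts. The event column would then repeat the subject column in those rows, and the totals in the overall table would still be uncovered.

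**Conclusion.** The point holds for event counts and nothing wider. As written, the plan counts an event with k recorded changes as k+1 AEs, in the overall summary (including its severity split) and in the event columns of the other AE tables. Subject counts and percentages are unaffected.

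The size cannot be given, because it depends on how often AEs fluctuate. It is zero if none do. The 12% to 50% illustration assumes one event with two recorded changes, both counted, on totals of 17 and 4. A reader might take only the smaller totals and quote 29% to 50% as the expected inflation. That range leaves out the larger totals and, like the full range, rests on a hypothetical event.

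A reader might also conclude that recovery from moderate to mild is certain to appear as a new AE. The documents are inconsistent on this: Protocol 9.4.1 opens the record, while the SAP's account of the database leaves no place for it. That mismatch is itself worth correcting, since the SAP rests its equation of AEs with treatment-emergent AEs on that account.

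**What to change.** In SAP 13.1:

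1. Link contiguous records of the same event within a subject, and count the linked episode once, at its maximum severity, wherever the number of AEs is shown. This carries over to events the worst-grade principle that the SAP already applies to subjects.
2. Keep the individual intensity and frequency records, with their dates, in the AE listing.
3. Reconcile the statement that "only AEs that begin or worsen after insertion of the IP will be captured in the database for this study" with Protocol 9.4.1, which also opens records for improvement and for any change in frequency.

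The cost is one derived linking variable in the AE analysis dataset, a few lines of SAP text, and slightly lower event totals. Site recording need not change, and the rule can be settled before database lock and unmasking. If linking is not adopted, the columns should at least be labelled as counts of AE records. That would describe the figure correctly but would not give the number of events.

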#### 9.4.2. **Serious Adverse Events**

Any SAE experienced by the subject from Visit 4b (Randomization/Insertion) through Visit 9 (30 day follow-up visit) is to be recorded on an SAE Form, regardless of the severity of the event or its relationship to study treatment.

Any SAE ongoing when the subject completes the study or discontinues from the study will be followed by the Investigator until the event has resolved, stabilized, or returned to baseline status.

#### 9.4.3. **All Events**

All events must be assessed to determine the following:

- If the event meets the criteria for an SAE as defined in Section 9.2.
- The severity of the event as defined in Section 9.7.1.
- The relationship of the event to study treatment as defined in Section 9.7.2.

CLN-Protocol-0052 Page **36** of **61** 

#### 9.5. **Immediate Reporting of Serious Adverse Events and Pregnancies**

In order to adhere to all applicable laws and regulations for reporting an SAE or pregnancy, the study site must formally notify the pharmacovigilance team within 24 hours of the study site staff becoming aware of the SAE or pregnancy. It is the Investigator's responsibility to ensure that the SAE or pregnancy reporting information is emailed or faxed as described in Figure 2. It may be necessary for the pharmacovigilance team to directly communicate with the Investigator if additional information is required.

After the initial SAE report, the investigator is required to proactively follow each subject and provide further information to the pharmacovigilance team on the subject's condition within 24 hours. New or updated information will be recorded on the SAE reporting form. The updated SAE reporting form should be sent to the pharmacovigilance team within 24 hours as described in Figure 2.

All additional follow-up evaluations must be reported to the pharmacovigilance team. Such data should be sent by fax or email (Figure 2) within 10 calendar days. All SAEs will be followed until the Investigator and Ocular Therapeutix agree that the event is satisfactorily resolved.

#### 9.6. Death

The death must be recorded on the appropriate eCRF. All causes of death must be reported as SAEs. The Investigator should make every effort to obtain and send death certificates and autopsy reports to the pharmacovigilance team.

Figure 2 **Reporting Information for SAEs and Pregnancies** 

To report initial or follow up SAE or Pregnancy information email or fax a copy of the SAE or Pregnancy report form to the following:

ProPharma Group

Email: [contact]

[contact]

#### 9.7. **Evaluating AEs and SAEs**

#### 9.7.1. Severity

The following definitions should be considered when evaluating the severity of AEs and SAEs:

- Mild Event is noticeable to the subject, but is easily tolerated and does not interfere with the subject's daily activities
- Event is bothersome, possibly requiring additional therapy, and • Moderate may interfere with the subject's daily activities
- Severe Event is intolerable, necessitates additional therapy or alteration of therapy, and interferes with the subject's daily activities

For AEs that change in intensity, the start and stop date of each intensity should be recorded.

An AE that is assessed as severe should not be confused with a SAE. An event is defined as 'serious' when it meets one of the pre-defined outcomes as described in Section 9.2 "Definition of a SAE."

CLN-Protocol-0052 Page **37** of **61** 

### 9.7.2. Relationship to OTX-DP or PV or procedure

The following definitions should be considered when evaluating the relationship of AEs and SAEs to the study treatment:

UNRELATED

This category applies to those (S)AEs which, after careful consideration, are clearly and incontrovertibly due to extraneous causes (disease, environment, etc.); there is no reasonable probability that the (S)AE may have been caused by the insertion procedure or the intracanalicular insert. If the investigator determines that the AE is unlikely to be related to the study drug, then this would be the appropriate category.

RELATED

The following criteria should be applied in considering inclusion of an (S)AE in this category:

- 1. It bears a reasonable temporal relationship to the insertion procedure or the presence of the intracanalicular insert
- 2. It could not be reasonably explained by the known characteristics of the subject's clinical state, environmental or toxic factors or other factors (e.g., disease under study, concurrent disease(s) and concomitant medications) and modes of therapy administered to the subject
- 3. It disappears or decreases on removal of the intracanalicular insert
- 4. It follows a known pattern of response to the insertion procedure or the intracanalicular insert

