### 9.9.3. Regulatory Reporting

Suspected Unexpected Serious Adverse Reactions (SUSARs) are SAEs that are unexpected and judged by the Investigator or Ocular Therapeutix to be associated to the study treatment administered. Ocular Therapeutix will report SUSARs to the appropriate authorities within the required regulatory timeframes. Reports of SUSARs will be made to IRBs, and Investigators, as needed.

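### The two relationship categories in Protocol Section 9.7.2 are neither exhaustive nor consistent, so allergy-like ocular events that the insert could also cause have no defined class

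*Protocol*

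**What the plan says.** Protocol Section 9.7.2 has two categories and no intermediate one.

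**UNRELATED** covers events that are "clearly and incontrovertibly due to extraneous causes (disease, environment, etc". It adds that "there is no reasonable probability that the (S)AE may have been caused by the insertion procedure or the intracanalicular insert". It then closes with a different threshold: "If the investigator determines that the AE is unlikely to be related to the study drug, then this would be the appropriate category".

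**RELATED** is introduced by "The following criteria should be applied in considering inclusion of an (S)AE in this category", followed by four points: (1) plausible timing; (2) no reasonable explanation in the subject's clinical state, environmental or toxic influences "or other factors (e.g., disease under study, concurrent disease(s) and concomitant medications"; (3) improvement when the insert is taken out; (4) a known pattern of response. The text does not say whether all four must hold.

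The judgement is used in two places. SAP Section 13.1 plans summaries of "All AEs suspected to be related to the IP", the same for serious events, and a breakdown by relationship. Protocol Section 9.9.3 defines SUSARs as "SAEs that are unexpected and judged by the Investigator or Ocular Therapeutix to be associated to the study treatment administered".

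**The concern.** This trial provokes allergic conjunctivitis on purpose while testing an insert whose listed risks (Section 4.5.2) include conjunctivitis, ocular pruritus, chemosis and allergic reaction. For such events the disease under study is a ready alternative explanation, and criterion 2 counts that against RELATED. Section 9.3 exempts no disease-related events from reporting, and Section 9.1 counts worsening of a pre-existing condition as an adverse event, so these events do reach the relatedness decision.

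If the two definitions leave such an event without a class, investigators must improvise. The only sentence that relaxes either threshold does so for UNRELATED; nothing correspondingly sends possibly related events to RELATED. The stake is the reliability of the related-event tables, for reactions that the protocol itself attributes to the insert.

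**Working it through.** The plan gives no figure for this point, so the check is to apply the definitions to three kinds of ocular event and then to see how widely the problem can reach.

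**1. Applying the definitions**

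| Event | Main UNRELATED definition | RELATED criterion 2 | Result |
|---|---|---|---|
| Explained only by the insert or procedure (for example, punctal stenosis) | Not met | Met | RELATED is available |
| Plainly extraneous | Met | Not met | UNRELATED |
| Explained by either allergy or insert (for example, chemosis on a challenge day) | Not met: cause not incontrovertible, insert causation reasonably probable | Not met: the disease under study is a reasonable explanation | Neither, if criterion 2 is required |

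For the third row:

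- If the four criteria are joint, the event fails RELATED on criterion 2 and also fails the main UNRELATED definition.
- If they are supportive, the investigator may choose RELATED, but the text does not say so.
- The unlikely sentence settles the matter only if the investigator judges a relation unlikely. It then conflicts with the incontrovertible standard in the same paragraph.

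Two investigators could class the same event differently and both claim to follow the text.

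**2. Criterion 3**

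Improvement on removal can be seen only if an insert is removed and the eye is observed afterwards. Inserts are designed to resorb (Section 4.3), and subjects without symptoms may leave Visit 9 with inserts in place (Section 8.13). Removal at Visit 9 coincides with exit, after which Section 9.4.2 provides follow-up for serious events; Section 9.4.1 has no matching sentence for other events. If all four criteria were required, criterion 3 alone would put RELATED out of reach for many events.

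**3. How many listed risks overlap with allergy**

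Section 4.5.2 lists 19 risks. My classification gives 7 that could be mistaken for an allergic response: pain or discomfort, conjunctivitis, epiphora, pruritus, allergic reaction, chemosis and inflammatory reaction. Blepharitis and impaired acuity are arguable, making 9.

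- 7/19 = 37%; 9/19 = 47%.
- The other 10 to 12, including canaliculitis, punctal stenosis, punctal trauma, IOP elevation and cataract, are not readily explained by allergic conjunctivitis.

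**4. How much of the reporting period the challenges cover**

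The six post-insertion challenges (Visits 5, 6a, 6b, 7, 8a, 8b) fall on Days 7, 8, 14 and 15. Adverse events are collected from Visit 4b (Day 1) to Visit 9 (Day 30, window to Day 33).

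- Challenge days: 4/30 = 13%, or 4/33 = 12%.
- Adding the day after each challenge (an assumption): Days 7, 8, 9, 14, 15, 16, so 6/30 = 20%.

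**5. Sensitivity of the tables**

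With 40 subjects per arm, moving one subject between classes changes that arm's related-event percentage by 1/40 = 2.5 points. Sections 4.2's three earlier allergic conjunctivitis trials had 4 to 17 adverse events per arm. Those are totals, not ocular or related events, so they show only that counts are small. The documents give no basis for estimating how many events would be misclassified.

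**The case against.** A reader might infer that RELATED is almost unattainable here and that insert-caused ocular events will be classed unrelated. The documents do not support that.

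- The strict UNRELATED definition does not capture an event with two plausible causes, and a possibly related event is not one judged unlikely to be related. The class is undefined, not determined.
- The four points are applied when considering the category and are not stated to be mandatory. The difficulty with criterion 3 itself favours reading them as guidance.
- Challenges occupy 4 of about 30 days. None falls on Days 1 to 6, just after insertion, or after Day 15. Subjects found with only one insert are not challenged further (Section 7.8). Many listed risks have no allergic explanation.
- All adverse events are recorded whatever their relationship (Section 9.4.1). Tables 14.3.1.2, 14.3.1.3, 14.3.1.8 and 14.3.1.9 do not use relatedness. The judgement is made masked, under the same schedule in both arms, and no inferential safety testing is planned (SAP Section 13).
- Serious events are reported within 24 hours regardless of relationship, and the sponsor may judge association independently of the investigator.

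All of this stands as a limit on scope, with one qualification to the calendar argument. Criterion 2 names the disease and the environment, not only the challenge. Every subject has a history of ocular allergies and positive skin tests to a perennial and a seasonal allergen, with antihistamines and mast-cell stabilizers disallowed. An allergic explanation can therefore be offered on other days too.

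It could also be objected that the RELATED criteria omit dexamethasone. That is a matter of clarity only: the OTX-DP insert contains the drug.

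**Conclusion.** The defect is real and limited. Section 9.7.2 sets two incompatible thresholds for UNRELATED, leaves the logic of RELATED unstated, and gives no rule for an ocular event that allergy and the insert could both explain. The likely consequence is inconsistent attribution, with a lean towards under-attribution because the only relaxing sentence leads to UNRELATED.

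It reaches Tables 14.3.1.4 to 14.3.1.7, 14.3.1.10 and 14.3.1.11, and the investigator's part in SUSAR decisions. It does not reach efficacy, the all-event tables or the severity tables. Systematic misclassification, in number or direction, is not shown.

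The conclusion rests on two assumptions: that investigators apply the definitions as written, and that allergy-like reactions are reported as adverse events, which Sections 9.1 and 9.3 permit. The 7 to 9 overlapping risks are my own classification. The correction is worth making because it is cheap and the tables concerned have small counts.

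**What to change.** In Protocol Section 9.7.2:

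1. Define UNRELATED as no reasonable possibility that the insert (including its drug) or the insertion procedure caused or contributed to the event, and RELATED as every other event. This makes the categories exhaustive.
2. Delete the sentence that sends unlikely events to UNRELATED.
3. State that the four RELATED criteria are supportive and that none is required.
4. State that a possible allergic explanation, from a challenge or from the environment, does not by itself make an event unrelated.

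Carry the wording into the eCRF guidelines, and add one line to SAP Section 13.1 saying that events suspected to be related are those classed RELATED. If events have already been classified under the present text, review them under the new rule before unmasking, so that the tables do not mix two standards.

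The cost is protocol and guideline wording, plus somewhat more events counted as related. Endpoints, sample size and study procedures do not change.
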